10.3.2 Analysis of Exploratory Efficacy Variables

The exploratory efficacy variables include the following:

- Natural History and Neuroprotection in Parkinson Plus Syndromes-Parkinson Plus Scale (NNIPPS-PPS) total score and dimensional scores
- Patient Global Impression of Change (PGI-C) score
- Letter Fluency Test (words per minute) score
- Repeatable Battery for Assessment of Neuropsychological Status (RBANS) total scale score and subtest scores
- Color Trails Test (Parts 1 and 2) completion time
- EuroQuality of Life (EQ-5D-3L) summary index score and VAS score
- Exploratory quantitative MRI measures including diffusion tensor imaging (DTI) derived fractional anisotropy (FA) and diffusivity measures [radial diffusivity (RD), mean diffusivity (MD), and axial diffusivity (AD)]

The MMRM method used for the primary efficacy analysis will be applied to analyze the change from the baseline to each post-baseline assessment up to the last visit of these exploratory variables with the exception of PGI-C for which the dependent variable is the PGI-C score itself. The model will include fixed, categorical effects for treatment, site, visit and treatment-by-visit interaction, with continuous fixed covariate for baseline score and the baseline score-by-visit interaction in the model. There is no baseline score and baseline score-by-visit interaction in the MMRM model for PGI-C analysis. The comparison will be the contrast between each ABBV-8E12 dose group and placebo group at each post-baseline visit.

The following statistics will be presented on the statistical table of MMRM analysis for change from baseline to each post-baseline visit: descriptive statistics (number of non-missing observations, mean, standard deviation, minimum and maximum) for each treatment group. LS mean and standard error within group will be presented for each treatment group. LS mean, standard error, 95% confidence interval and two-sided nominal *P* values of treatment difference comparing each ABBV-8E12 dose group with placebo will also be presented for each post-baseline visit. No multiplicity adjustment will be conducted for multiple comparisons of exploratory efficacy variables.

Responder analysis will be conducted for PGI-C variable. The responses of "Very much improved," "Much improved," "Minimally improved" and "No change" on the PGI-C will be defined as responders. Repeated measure analysis of responders over time on PGI-C responder status will be conducted using a GEE model with a logit link function to compare probability of being a responder between each ABBV-8E12 dose and placebo. The model will include fixed, categorical effects for treatment, site, visit and treatment-by-visit interaction using an exchangeable working correlation structure in the model. The odds ratio and corresponding 95% confidence interval will be provided for each dose group at each visit. This responder analysis will not be included in multiplicity adjustment for FWER.

10.4 Additional Efficacy Analysis

10.4.1 Listing of Randomized Subjects Not Included in the Primary Efficacy Analysis

A listing of the randomized subjects that were not included in the primary efficacy analysis will be prepared. The listing will include the reason(s) the subject was not included (did not receive study drug, had no baseline observation and/or had no post-baseline observation no more than 45 days after the last dose of study drug).

10.4.2 Combination of Sites with Fewer Than 2 Subjects per Treatment Group

When "site" is included as a factor in a statistical model for the interim or final analyses, Japan is considered as one site because randomization is stratified by country for Japan. In countries other than Japan, sites that do not have at least 2 subjects per treatment group for the ITT dataset will be combined within each country as follows.

1. Divide the sites into 2 groups with Group 1 including all sites that have at least 2 subjects per treatment group and Group 2 including all remaining sites. Sort each group in ascending order by total sample size and investigator number.
2. Starting at the top of the Group 2 list (i.e., the first site with the smallest sample size), combine the minimum number of sites required to achieve a pseudo-site that has at least 2 subjects per treatment group. Continue this process until all Group 2 sites have been grouped into pseudo-sites.
3. If there is a site (or sites) left after Step 2, combine this site (or sites) with the last pseudo-site that is created. For the situation where there is no previous pseudo-site exists, combine this site (or sites) with the first site on the sorted Group 1 list.

The naming of the pseudo-sites will be given by xxx99901, xxx99902, etc., where xxx is the country code.

The combined pseudo-sites will be used in all statistical models that include the "Site" as a factor. However, the original site identification will be used in all summaries of subject disposition or discontinuation by Study Site and in all data listings. In the summaries of the number and percentage of subjects contributed by each site in each treatment group for the ITT dataset, the name of pseudo-sites will also be displayed.

10.5 Handling of Missing Data for Efficacy Assessments and Sensitivity Analysis of the Primary Efficacy Endpoint

Missing Items for a Rating Scale

Unless otherwise specified, when a total or domain score of an efficacy measure is calculated from a set of individual items, the total or domain score will be considered missing if any of the individual items are missing. When an average score is obtained from a set of individual items, it will be calculated from the non-missing items. Missing items will be imputed specifically for the following scales:

- UPDRS Part II: if no more than 15% of items are missing for an assessment, i.e., if 1 item has missing answer, the missing item will be imputed using the mean of non-missing items' scores for the assessment. If 2 or more items are missing for an assessment, the items' score will not be imputed and UPDRS Part II score is missing.
- NNIPPS-PPS:
 - Total score: if no more than 15% of all items are missing for an assessment, i.e., if less than or equal to 12 items are missing, each item score is imputed using the mean value of the same item from subjects of the same treatment group whose data are not missing for the item at the same visit. NNIPPS-PPS total score will be calculated based on this imputation but dimensional scores will not be calculated from this imputation. If more than 12 items of NNIPPS-PPS for an assessment for a subject are missing, then those items will not be imputed and the NNIPPS-PPS total score will be missing. Dimensional scores without any missing items will not be missing.
 - Dimensional score: if no more than 15% items for a dimension is missing, then each item score is imputed using the mean value of the same item from subjects of the same treatment group whose data are not missing for the item at the same visit. If more than 15% of all items for the dimension are missing, then those items will not be imputed and the dimensional score will be missing. After the imputation of this step, dimensional scores

will be calculated and used in dimensional score analysis, total score will not be calculated based on this imputation.

- PSP-QoL
 - Missing VAS score will not be imputed.
 - Total score: If no more than 15% of the 45 items, i.e., less than or equal to 6 items are missing for an assessment, each item score is imputed using the mean value of the same item from subjects of the same treatment group whose data are not missing for the item at the same visit. If more than 6 items of PSP-QoL for an assessment for a subject are missing, then those items will not be imputed and the PSP-QoL total score will be missing. After the imputation in this step, subscale scores won't be calculated and only the total score will be added up and used in total score analysis.
 - Subscale score: if no more than 15% of all items are missing in a subscale, each item score is imputed using the mean value of the same item from subjects of the same treatment group whose data are not missing for the item at the same visit. If more than 15% of all items for a subscale are missing, then those items will not be imputed and the subscale score will be missing. After the imputation of this step, subscale scores will be calculated and used in subscale score analysis, the total score will not be calculated based on this imputation.

Missing Visit Data

Before conducting any imputation of missing visit data, patterns of missing data for the primary endpoint PSPRS total score changes in placebo and two ABBV-8E12 arms will be assessed. Observed mean changes from baseline in PSPRS total score will be summarized over time for different missing patterns of longitudinal data (discontinued after Week 12 assessment, discontinued after Week 24 assessment, discontinued after Week 36 assessment, completer). Number and percentage of subjects for each missing pattern will be summarized as well.

10.5.1 Sensitivity analysis accounting for missing data

To evaluate robustness of the primary efficacy results on PSPRS total score changes from baseline, sensitivity analysis of PSPRS total score changes will be conducted using a multiple imputation (MI) assuming monotonic missing in this study. Sensitivity analysis will be conducted only if at least one ABBV-8E12 dose is statistically significant different from the placebo with multiplicity adjustment in the primary efficacy endpoint analysis.

Sensitivity analyses using MI will be conducted in the following three steps:

1. Using Monte Carlo Markov Chain (MCMC) methodology from PROC MI to impute the intermittent missing data to achieve a monotone missing pattern by treatment group;
2. Impute missing data to create 20 complete datasets including observed completers and imputed data for PSPRS total score changes from baseline using the MI method;
3. Analyze each imputed dataset generated in Step 1 with the same analysis model for the primary efficacy analysis of the primary endpoint and keep analysis results for each imputed dataset;
4. Combine analysis results across imputed datasets.

The multiple imputation (MI) method will be used to impute missing data at various visits overtime. The MI method will be applied separately for each ABBV-8E12 dose arm and placebo arm. Multivariate regression models will be used to impute PSPRS total score missing data for different visits. To impute missing values for PSPRS total score for Visit X, variables included in the impute model are baseline PSPRS total score, PSPRS total score before discontinuation at Visit X, investigator site. A mean vector and variance covariance matrix based on all available cases will be used for the imputation. If the monotonic missing pattern is not satisfied, the MCMC method will be used to create monotonic missing pattern by filling missing values between visits where data are observed. Imputed PSPRS total score needs satisfy the range requirement for the scale

(0 to 100). The MI will be implemented using PROC MI in SAS 9.4. In Step 3, SAS PROC MIANALYZE procedure will be used to combine MMRM analysis results based on 20 imputed datasets.

The following analysis results will be presented for the sensitivity analysis with multiple imputations: LS mean difference between ABBV-8E12 doses and placebo, standard error, 95% confidence interval of LS mean difference at Week 52 based on imputed data including observed data and p-values comparing ABBV-8E12 doses against placebo. Parameters based on imputed dataset will be combined estimation across 20 imputed datasets using Rubin's rules.

Tipping-point sensitivity analysis using multiple imputations to impute missing data will also be performed to evaluate robustness of primary analysis results for PSPRS total score changes from baseline if missing data deviate from the missing at random (MAR) assumption. A total of 20 imputed datasets will be generated using MI for each shift parameter. The shift parameter k indicates the percentage of treatment group difference (Δ) between ABBV-8E12 and placebo for PSPRS total score change obtained in the primary MMRM analysis that is not maintained for the MI sensitivity analysis. For each k , the imputation will be carried out by subtracting $k*\Delta$ from imputed missing data for those treated subjects in ABBV-8E12 groups after dropout. The imputation will be conducted with corresponding visit specific $k*\Delta$ for missing data after dropout. The values of k range from 0% to 100% or higher in 10% increments. The first value of k that reverses the study conclusion is considered the tipping point. The treatment group differences and associated p-values from tipping point analysis for each value of k will be presented.

The tipping point analysis will be conducted in the following steps:

1. Using Monte Carlo Markov Chain (MCMC) methodology from SAS PROC MI by treatment group to impute the intermittent missing data to a monotone missing pattern;

2. Using a standard multiple imputation approach from SAS PROC MI to impute data from monotone missing data;
3. For subjects who have missing data in the ABBV-8E12 groups, a shift which is equal to $k \cdot \Delta$ will be subtracted for imputed values in Step 2 after the dropout, with k described in the above. For subjects in the placebo group, no shift will be performed for missing data after dropout;
4. Using MMRM model for the primary efficacy endpoint analysis to analyze the observed data along with the imputed data from Step 3 for PSPRS total score change from baseline;
5. Obtaining the overall results using PROC MIANALYZE for each shift parameter k using Rubin's rules.

The following analysis results will be presented by the shift parameter k for the tipping point analysis: LS mean difference between ABBV-8E12 doses and placebo, standard error, 95% confidence interval of LS mean difference at Week 52 based on imputed data including observed data and p-values comparing ABBV-8E12 doses against placebo.

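### SAP 10.5.1: item 3 of the multiple-imputation list sends the MMRM to the Step 1 data sets, where dropouts are still missing, instead of the 20 complete data sets from Step 2

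*SAP*

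**What the plan says.** The MI sensitivity analysis in SAP 10.5.1 is given as a numbered list followed by explanatory text. The list is introduced with "Sensitivity analyses using MI will be conducted in the following three steps", and four items follow:

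1. MCMC fills the gaps between observed visits: "impute the intermittent missing data to achieve a monotone missing pattern by treatment group".
2. The values after dropout come next: "Impute missing data to create 20 complete datasets including observed completers and imputed data". The variable imputed is the PSPRS change from baseline.
3. The analysis is then specified: "Analyze each imputed dataset generated in Step 1 with the same analysis model for the primary efficacy analysis of the primary endpoint". Results are kept for each data set.
4. The results are combined over the imputed data sets.

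The explanatory text describes an imputation model fitted separately in each arm, with baseline PSPRS, earlier PSPRS scores and site as predictors. It ends: "In Step 3, SAS PROC MIANALYZE procedure will be used to combine MMRM analysis results based on 20 imputed datasets". The description of outputs asks for the "confidence interval of LS mean difference at Week 52 based on imputed data including observed data", with parameters taken as a "combined estimation across 20 imputed datasets" under Rubin's rules.

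The section opens by making the sensitivity analysis conditional: it is run only if at least one dose beats placebo on the primary endpoint after multiplicity adjustment.

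**The concern.** Items 2 and 3 do not connect. Item 2 produces the data sets in which every subject has a Week 52 value. Item 3 passes over them and names the output of item 1, where anyone who dropped out still has no value from the dropout visit onward. A programmer who follows the numbering would fit the primary MMRM to data that differ from the observed data only where an intermittent gap was filled. The SAP's Introduction gives guiding the programming work as one of its purposes, so a step reference is an operative instruction.

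The MI analysis is meant to show that a positive primary result does not depend on how missing Week 52 data are handled. A version that leaves those data missing cannot show that. Its close agreement with the primary result would carry almost no information, yet it could be read as evidence of robustness.

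**Working it through.** The plan states no figure on this point, so there is nothing to reproduce. The check has two parts: a reading of the steps against each other, and an illustration of what the reference changes.

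**Reading the steps**

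| Item in SAP 10.5.1 | What it produces or uses | Week 52 values of dropouts |
|---|---|---|
| Step 1 | Data with a monotone missing pattern; number of data sets not stated | Still missing |
| Step 2 | 20 complete data sets | Imputed |
| Item 3 as written | Uses the Step 1 output | Still missing |
| Item 4, output text | Pools over 20 imputed data sets, imputed plus observed data | Imputed, on the natural reading |

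Within the list, both the number 20 and the description of the data sets as complete belong only to Step 2. Two other numbering slips point the same way: three steps are announced and four listed, and the text places the pooling at Step 3 although it is item 4. All three slips fit a three-step list (impute, analyse, combine) to which the MCMC step was added at the front without renumbering. The tipping-point list later in the same section is numbered consistently: its Step 3 shifts the Step 2 values and its Step 4 analyses the Step 3 data.

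**How many subjects are concerned**

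SAP 4.3 assumes 25% without data at Week 52. 0.25 × 330 = 82.5 subjects, or 0.25 × 110 = 27.5 per arm. This is a planning count of those whose Week 52 value the MI is meant to supply. It is not an effect on any estimate.

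**Illustrative simulation**

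- From the documents: 110 per arm; PSPRS at Weeks 12, 24, 36 and 52; effect sizes 0.56 and 0.28 (SAP 4.3); 20 imputations; Rubin's rules.
- Assumed, not in the documents: Week 52 SD 10; placebo change 11 points; correlation 0.75 per visit step; missing-at-random (MAR) dropout, averaging 19% missing at Week 52; about 3% intermittent gaps at Weeks 24 and 36.
- Model: MMRM with unstructured covariance and visit-specific treatment and baseline effects, without a site term. Step 1 was MCMC by arm, Step 2 monotone regression by arm.
- 20 simulated trials.

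Pooling with m = 20: the estimate is the mean over imputations, and the total variance is W + (1 + 1/20)B, where W is the average within-imputation variance and B the between-imputation variance.

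| High dose minus placebo, Week 52 | Mean estimate | Mean SE | Mean absolute gap to primary | Maximum gap | SE ratio to primary |
|---|---|---|---|---|---|
| Primary MMRM | −5.24 | 1.46 | – | – | – |
| Item 3 as written (Step 1 data) | −5.24 | 1.46 | 0.003 | 0.007 | 1.000 |
| Item 3 corrected (Step 2 data) | −5.28 | 1.48 | 0.18 | 0.75 | 1.015 |

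After Step 1, an average of 64 of 330 subjects still had no Week 52 value.

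The between-imputation variance shows the mechanism:

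- Step 1 data: B = 0.000165, so 1.05 × 0.000165 = 0.00017, against a total variance of about 1.46² = 2.13. The imputation contributes essentially nothing.
- Step 2 data: B = 0.323, so 1.05 × 0.323 = 0.34, against about 1.48² = 2.19, roughly 15%.

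Part of the 0.18-point gap is simulation noise from using 20 imputations: √(0.323/20) = 0.13 points.

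**The case against.** The strongest reply is that this is a numbering slip which the surrounding text corrects. Three statements in SAP 10.5.1 require the intended analysis: Step 2 creates the 20 complete data sets, the pooling sentence combines MMRM results from 20 imputed data sets, and the output text bases the Week 52 difference on imputed plus observed data. Most of this stands. A reader might infer from item 3 that the completed data sets are never analysed; taken as a whole, the section does not say that. What remains is that item 3 is the only sentence naming which step's output enters the MMRM, and it names the wrong one. Because Step 1 gives no number of data sets, the other phrases make the intent clear without strictly excluding the wrong reading.

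A second reply is that close agreement with the primary MMRM is not peculiar to the error. That also stands. The intended MI assumes MAR, as the MMRM does, so it should land nearby in any case. A reader might infer that the slip alone guarantees agreement. The agreement would be near-exact rather than guaranteed, because intermittent gaps are filled, and the corrected version would usually agree closely too.

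Third, the tipping-point analysis starts at k = 0%, where no shift is applied. Its steps are referenced correctly, so it would deliver essentially the intended unshifted MI result even if item 3 were programmed literally. This stands and limits the damage. It also means that the literal version would fail an obvious internal check: the MI result and the k = 0% result should match apart from imputation noise.

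**Conclusion.** The cross-reference in item 3 is wrong as written and should be corrected; the severity is minor. The textual finding needs no assumptions, since Step 1 by its own description leaves post-dropout values missing. The size of the consequence rests on the simulation's assumed variances, correlations and MAR dropout. There, the literal reading moved the high-dose estimate by about 0.003 points from the primary MMRM and the corrected reading by about 0.18 points, on an effect of about 5.2 points. Other assumptions would change these values, but under MAR both gaps should stay small relative to the effect.

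The error does not touch the primary MMRM, alpha, the graphical testing procedure or the tipping-point analysis, which is where departures from MAR are tested. Nor should the 82.5 subjects be read as lost from the plan's missing-data assessment. They are the expected number to be imputed, and the documents do not show that any estimate or conclusion would change.

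**What to change.** In SAP 10.5.1, make three edits to the MI sensitivity analysis:

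- Item 3: change the reference from Step 1 to Step 2.
- Introduction to the list ("will be conducted in the following three steps"): change three to four.
- Pooling sentence ("In Step 3, SAS PROC MIANALYZE procedure will be used to combine MMRM analysis results based on 20 imputed datasets"): change Step 3 to Step 4.

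The cost is three words in the SAP, with no change to design, data collection or any other analysis. It should be done before programming and unblinding. The corrected MI should be reported as a second analysis under MAR; evidence on departures from MAR should come from the tipping-point analysis.

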4.3 Sample Size

Approximately 330 PSP subjects (110 subjects/group) will be enrolled and randomized into two ABBV-8E12 dose groups and the placebo group with 1:1:1 randomization ratio. This sample size has ~90% power to detect an ABBV-8E12 effect size (vs. placebo) of 0.56 for the high dose and 0.28 effect size for the low dose on the PSPRS total score changes from baseline at Week 52 using the Bonferroni method to control for multiplicity due to multiple comparisons between two doses and placebo at the two-sided 5% significant level. A no data rate of 25% at Week 52 is assumed in this sample size calculation using East version 6.3.1 (Cytel).

In Japan, a total of 24 subjects (8 subjects/arm) randomized will have 80% probability to detect the consistent treatment effect among three regions (Japan, North America including US/Canada, and European countries including Australia assuming 7%, 54%, and 39% of the total 330 PSP subjects are randomized in three regions, respectively). This calculation is based on Method 2¹ and assumes that the significance level for comparison of each ABBV-8E12 dose vs. placebo is two-sided 2.5% and the dropout rate is 25% in all regions.

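### Twenty imputations per shift are too few for a tipping point read off a 10-point grid: its seed-to-seed SD is roughly 7 to 23 points

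*SAP*

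**What the plan says.** SAP 10.5.1 plans a tipping-point analysis of the PSPRS change at Week 52. Imputed values of ABBV-8E12 dropouts are moved by k times the treatment difference Δ from the primary MMRM. Placebo is imputed but not moved: "For subjects in the placebo group, no shift will be performed for missing data after dropout".

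- Number of imputations: "A total of 20 imputed datasets will be generated using MI for each shift parameter".
- Grid: "The values of k range from 0% to 100% or higher in 10% increments".
- Reported figure: "The first value of k that reverses the study conclusion is considered the tipping point".
- Output: "The treatment group differences and associated p-values from tipping point analysis for each value of k will be presented".
- Trigger: "Sensitivity analysis will be conducted only if at least one ABBV-8E12 dose is statistically significant different from the placebo".

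The section states no random seed and no limit on Monte Carlo error. It does not settle whether the imputations are redrawn at each k. The sentence on 20 datasets ties them to each shift, which read literally means fresh draws. The numbered steps impute first (Step 2) and subtract the shift from those imputed values afterwards (Step 3), which also allows one set shared over all k.

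**The concern.** A tipping point is only as precise as the p-values either side of it. Here the shift reaches only the missing quarter of the active arm, so a 10-point change in k moves the pooled estimate very little. Twenty imputations leave random error in both the pooled estimate and its standard error. If that error is about as large as one grid step, the reported k depends partly on the seed, and the 10-point grid claims more resolution than the method has.

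What is at stake is the robustness statement attached to a positive primary result: how much of the treatment effect dropouts could lose before significance goes.

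**Working it through.** **Inputs.** 110 per arm, effect size 0.56 for the high dose, 25% no data at Week 52 and about 90% power (SAP 4.3). Final α 0.04998 split equally over two doses, so 0.02499 two-sided per dose and critical |z| 2.24 (SAP 10.6). m = 20 and 10-point steps (SAP 10.5.1). The fraction of missing information (FMI) depends on the correlation of PSPRS between visits, which neither document gives. I take FMI 0.05 to 0.25 as an assumption.

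**The plan's own figure.** Evaluable n per arm = 110 × 0.75 = 82.5. SE = √(2/82.5) = 0.1557 SD. z = 0.56/0.1557 = 3.60. Power ≈ Φ(3.60 − 2.24) = 0.91, which agrees with the stated 90% or so.

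**Size of one grid step.** A step moves the estimate by 0.10 × 0.25 × Δ = 0.025Δ, so z moves by 0.025 × Δ/SE.

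- True tipping point 50%: Δ/SE = 2.24/(1 − 0.25 × 0.50) = 2.56, step 0.064.
- Design effect: Δ/SE = 3.60, step 0.090. The tipping point is (1 − 2.24/3.60)/0.25, about 151%.

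**Monte Carlo SD of z.** By Rubin's rules the pooled estimate has Monte Carlo variance B/m, which is FMI/m in squared SE units when FMI is approximated by B/T. The estimated B has relative SD √(2/(m − 1)), which carries into the SE at half weight:

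SD(z) = √[ FMI/m + (0.5 × FMI × √(2/(m − 1)) × 2.24)² ]

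At m = 20 and FMI 0.25 this is √(0.0125 + 0.0083) = 0.144.

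| FMI | SD(z), m = 20 | in grid steps, tipping point 50% | in grid steps, design effect |
|---|---|---|---|
| 0.05 | 0.053 | 0.83 | 0.59 |
| 0.10 | 0.079 | 1.24 | 0.88 |
| 0.15 | 0.102 | 1.60 | 1.14 |
| 0.25 | 0.144 | 2.25 | 1.60 |

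One grid step is 10 points, so the extremes are 5.9 and 22.5 points. Rounding to the grid adds an SD of about 10/√12 = 2.9 points: √(5.9² + 2.9²) = 6.6 and √(22.5² + 2.9²) = 22.7. That is roughly 7 to 23 points.

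**Check by simulation.** Four visits, 110 per arm, monotone 25% dropout, regression imputation by arm, Week 52 ANCOVA in place of the full MMRM, Rubin pooling, α 0.02499. With m = 20, visit correlation 0.3 to 0.9 and a limiting tipping point of 50% or 100%:

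- Fresh draws at each k: SD 9 to 17 points, limiting grid value reported in 16 to 41% of runs, non-monotone reversals in 20 to 68%. The mean is too low in most settings; at FMI 0.25 it was 34% against a limit of 50%.
- One shared set: SD 10 to 24 points, limiting grid value in 16 to 37% of runs, mean within about 0 to 5 points of the limit, mostly grid rounding.

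At correlation 0.95, or 0.9 at the design effect, noise falls below or close to one step, yet the limiting value is still reported in only about 38 to 62% of runs.

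**Effect of more imputations.** From the formula at a true tipping point of 50%, in points:

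| m | FMI 0.10 | FMI 0.15 | FMI 0.25 |
|---|---|---|---|
| 20 | 12 | 16 | 22 |
| 200 | 4 | 5 | 7 |
| 500 | 2.5 | 3.2 | 4.5 |

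From simulation with one shared set, SD in points and share of runs reporting the limiting value:

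| Correlation, limit | m = 20 | m = 200 | m = 500 |
|---|---|---|---|
| 0.6, 20% | 18.1; 15% | 7.5; 46% | 5.5; 61% |
| 0.6, 150% | 14.7; 28% | 4.8; 79% | 2.7; 92% |
| 0.9, 150% | 8.6; 46% | 2.1; 96% | 0.9; 99% |

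**The case against.** Four things can be said for the plan.

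1. *Noise need not exceed the grid step.* A reader might infer that it always does. The documents do not support that, because they give no visit correlation. Noise exceeds one step only above an FMI of about 0.07 to 0.08 when the tipping point is near 50%, and above about 0.12 to 0.13 at the design effect. With strongly correlated visits it can be smaller. This stands, and the result is therefore given as a range.

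2. *A downward bias is not established.* A reader might infer that the reported tipping point is too low as a matter of course and the p-values non-monotone. Both arise from taking the first crossing over independent draws at each k. Steps 2 and 3 equally allow one shared set, with which no material bias appears. The bias is conditional; the spread is not.

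3. *The consequence is limited.* The analysis runs only after a significant primary result and changes no test. The SAP sets no k that counts as robust. The difference and p-value are shown at every k, so a ragged pattern would be visible. If the tipping point lies well above 100%, an error of 10 or 15 points hardly changes its reading. All of this stands. Even so, the SAP defines the reported figure as the first crossing, and seeing a ragged pattern does not alter that figure. Near 50% the spread does affect interpretation.

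4. *A seed stored in the program makes the number repeatable.* True, but it does not make it precise. Another equally valid seed can give another grid value.

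**Conclusion.** The point holds as one of precision. With m = 20 and 25% missing at Week 52, the reported tipping point carries a seed-to-seed SD of roughly 7 to 23 percentage points, from about one to more than two grid steps. This is so whether imputations are redrawn at each k or shared. If they are redrawn, the first crossing also tends to be too low, by about 5 to 15 points at the higher fractions of missing information.

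The size rests on an assumed FMI of 0.05 to 0.25, on normal change scores with equal SD, and on treating the Week 52 contrast as an ANCOVA. The step size follows from the SAP's own figures.

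A reader might go on to doubt the primary conclusion. Nothing here bears on it: the primary MMRM, its α and the testing order are unaffected. This is an inexpensive improvement to a sensitivity analysis, worth making before unblinding.

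**What to change.** In SAP 10.5.1, replace the sentence on 20 datasets for each shift with the following provisions:

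- One set of at least 200 imputed datasets, preferably 500 or more, is generated once under missing at random, with the seed recorded.
- Every k is applied to that same set.
- The Monte Carlo error of the estimate and p-value is reported at the grid values around the crossing.

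At 200 the SD of the reported k is about 4 to 7 points for FMI 0.10 to 0.25 and a tipping point near 50%; at 500 it is about 2.5 to 4.5. Sharing the set also removes the low bias that fresh draws would bring, but sharing only 20 does not cure the spread.

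The cost is one amended paragraph and computing time. No estimand, α or primary model changes. Raising the number for the separate missing-at-random analysis is optional: it has no grid and no first-crossing rule, and this point does not require it.
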